### 5.3 Missing data

The mixed effects model as chosen model class is comparatively robust regarding missing data. In addition an analysis using multiple imputation of missing data in baseline variables will be performed as sensitivity analysis.

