### 2.2 Randomization

A randomising sequence is created (boxes for 97 patients with probabilities for each condition derived from estimated prevalences and two test entries – 999 total boxes) not being SAP **2.0**

accessible for neither study nurse nor GP at any given point. After a patient has finished the baseline measurement, reached a PHQ-9 score higher than 9, randomisation happens electronically (allocation concealment). Patients are stratified by their depression severity (moderate and severe). The study is not cluster-randomised, as within every single GP's office each of the three conditions is realised and therefore an individual randomisation of patients is feasible.

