### 2.3 Sample size

The sample size calculation is based on the results of the preliminary study called DEPSCREEN-INFO, which showed an effect of Cohen's  $d = 0.27$ . In this study a lower effect of  $d = 0.25$  for the intervention group compared to the other groups is supposed. The sample size was calculated for an ANOVA based on the F-test. Because of the closed test principle, in case of a significant result in this overall test, the pairwise comparisons can be performed without adjustment of the type-I error. To detect the underlying effect size through an F-test with a significance level of  $\alpha = 0.05$ , a power of  $1-\beta = 0.8$  and group effects 0 and 0.25 a sample size of  $n = 233$  is needed in every group (balanced design). This adds up to a total sample size for the actual enrolment of  $N = 699$  (computations were made with PASS 2008). The estimated prevalence of depressive disorders in a GP's office is 15%. 50% of all participants of the depression screening are not going to be eligible to further participate in the study as they achieve a lower PHQ-9 score than 10. Based on previous work a loss of 35% of included patients at the time of the 6-months follow-up is expected. Therefore, 1074 patients have to be included in the study in order to roughly maintain 699 patients for the primary analysis. Five study centres with each 10 GP's offices therefore have to include at least 14320 patients in the study. Thus, in every GP's office 287 patients (rounded from 286.4) will be screened on average. 30 patients will be asked to participate at each GP's office per day whereas only 15 of them consent and are eligible for the study. The total recruitment length then adds up to  $14350 / (15*5) = 192$  recruitment days if patients will be recruited simultaneously in all 5 centres. Considering weekends leads to  $192 * (7/5) = 269$  days or 39 weeks of recruitment. To take unforeseen recruitment problems into consideration the total length is extended to 12 months.

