# 3 Statistical Principles

## 3.1 Confidence intervals and *P* values

The level of statistical significance is 5% two-sided. Because of the closed testing principle, the pairwise comparisons of the three groups do not have to be adjusted for multiplicity if the overall test yields a significant result. Accordingly, all applicable statistical tests will be two-sided and will be performed using a 5% significance level. Analyses of secondary outcomes will be performed without adjustment for multiplicity. All confidence intervals presented will be 95% and two-sided.

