## 4.4 Withdrawal/follow-up

An already accepted patient is withdrawn from the study if the patient withdraws his consent. The study nurse records these events and reports them to the principal investigator. There are three follow-ups planned. The 6-months follow-up is the main one collecting data for both primary and secondary endpoints. The 1-month and 12 months follow-up are only collecting data for secondary endpoints. It is estimated that 35% of the included patients in every group will be lost for the 6-months follow-up. In case of acute suicidality during the follow-up telephone interviews the interviewers will be advised to stop the interview and contact professional help by use of a second phone.

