### 5.2 Analysis methods

#### 5.2.1 Analysis of primary endpoint

The primary outcome of all randomised patients will be analysed regarding the intention-to-treat principle and according to the memorandum of the DFG about good clinical practice all study results are going to be documented and published.

Primary outcome: depression severity (PHQ-9 score) 6 months after intervention as change from baseline. The primary outcome is going to be analysed via a mixed effects model including random effects patients and GP practices nested in centres and fixed factors for group and depression severity. The baseline comparisons will be represented by statistical contrasts. The use of the closure test ensures a familywise significance level of 5% if the p-value of the overall test is below 0.05.

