#### 5.2.2 Analysis of secondary endpoint

The secondary outcomes are health care use (e.g., visiting a doctor, medication), direct and indirect costs, depression severity after one and 12 months (PHQ-9), diagnosis of depressive disorder according to MINI structured interview, anxiety (GAD-7), somatic symptom severity (SSS-8) and quality-adjusted life years (QALYs). Secondary endpoints will be analysed with the data collected in the 1-month, 6-month, and 12-months follow-up like the primary endpoint. Adjusted and non-adjusted means, effect sizes (Cohen's d) and confidence intervals will be reported.

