#### 5.2.3 Additional analysis

As additional exploratory analyses, subgroup analyses based on several demographic and clinical values are conducted w.r.t. change of PHQ-9 score. The aim of these analyses is to identify subpopulations, which benefit more or less from the intervention. These analyses shall give a first starting point for future studies. Missing values will not be imputed, but the implicit MAR assumption of the analysis model will be used.

The presented p-values are of descriptive nature only (two-sided tests at unadjusted significance level of 5%). The analyses are conducted in the FAS.

For the analyses on a potential interaction between the intervention and age (continuous, and categorical: young [ $\leq$ first tercile] vs. old [ $>$ third tercile]), sex (men vs. woman), depression history (previous episode vs. no history of depression), other mental health comorbidity (mental health comorbidity vs. mental health comorbidity), city size (ordinal), education ( $\leq$  10 years in school vs.  $>$  10 years in school), living situation (living together vs. alone), insurance status (private vs. statutory health insurance), reason for GP visit (psychological vs. physical), migration background (migration background vs. no migration background), quality of life at baseline (continuous and dichotomized with median as cut-off point; based on the visual analogue scale of the EQ-5D), anxiety disorder (yes vs. no), substance disorder (yes vs. no), chronic physical disease (yes vs. no), persistent somatic symptoms (yes vs. no), mood swings (yes vs. no), social support (yes vs no), pregnancy in female patients (yes vs. no) and breast feeding in female patients (yes vs. no) on the change in PHQ-9 score from baseline to month 6, the regression models and their parameters are defined analogously to the primary analyses but additional effects for demographic and clinical values and its interaction with the treatment are added to each model.

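### About 35% of 6-month PHQ-9 scores are expected to be missing, but no planned analysis tests the primary result against a departure from MAR, and SAP 5.2.1 leaves open which visits enter the model

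*SAP*

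**What the plan says.** **Expected loss.** SAP 2.3 states that "a loss of 35% of included patients at the time of the 6-months follow-up is expected", and enrols 1074 to keep roughly 699. SAP 4.4 applies the rate to each arm: "It is estimated that 35% of the included patients in every group will be lost for the 6-months follow-up". The primary population (3.3.1) is everyone randomised.

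**Handling of missing data.** SAP 5.3 regards the mixed model as fairly robust to missing data and adds one sensitivity analysis: "In addition an analysis using multiple imputation of missing data in baseline variables will be performed as sensitivity analysis". MAR is named only for the exploratory subgroups in 5.2.3: "Missing values will not be imputed, but the implicit MAR assumption of the analysis model will be used".

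**Primary model.** SAP 5.2.1 specifies "a mixed effects model including random effects patients and GP practices nested in centres and fixed factors for group and depression severity". It lists no visit or group-by-visit term and does not say which follow-up scores enter. SAP 5.2.2 adds: "Secondary endpoints will be analysed with the data collected in the 1-month, 6-month, and 12-months follow-up like the primary endpoint". SAP 4.4, on the other hand, assigns the 1- and 12-month contacts to secondary endpoints only.

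**Gate.** Under SAP 3.1, "the pairwise comparisons of the three groups do not have to be adjusted for multiplicity if the overall test yields a significant result".

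**Baseline data.** Under SAP 2.2 the score comes first: once a patient has "reached a PHQ-9 score higher than 9, randomisation happens electronically", stratified by severity.

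**The concern.** The planned sensitivity analysis is aimed at the wrong variables. The baseline PHQ-9 decides eligibility and stratum, so it exists for every randomised patient, as does the group. Imputing other baseline variables leaves the listed primary model unchanged. The values expected to be absent in large numbers are the 6-month scores, and nothing planned varies the assumption made about them. If the primary result is significant, a reader could not tell how far that depends on MAR for about a third of the patients.

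The model description adds a second uncertainty. How much the mixed model protects against missing outcomes, and what its group coefficient estimates, both depend on whether only month 6 or several visits enter. The SAP can be read either way.

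**Working it through.** **1. The plan's own sample size.** Inputs from SAP 2.3: three arms, effects 0, 0 and 0.25 SD, alpha 0.05, 233 per arm. Noncentrality = 233 × (2/3) × 0.25² = 9.71. Critical F(2, 696) = 3.009. Power = 0.801, so 233 per arm is reproduced.

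**2. Missing outcomes.** 1074 − 699 = 375. Per arm, 1074/3 = 358 enrolled, and 358 × 0.35 ≈ 125 are without a 6-month score.

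**3. Reach of the planned check.** The listed fixed factors are group and severity stratum. The outcome is the change from baseline to month 6. Group, stratum and baseline PHQ-9 are all known at randomisation (2.2). Only the 6-month score can be missing, and 5.3 does not impute it.

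**4. Tipping point with the completers' standard error.** Assumptions: the two comparison arms are equal, SD is 1, and only the feedback arm's missing scores are worse than assumed, by delta SD.
- With means 0, 0 and d, F = n·d²/3. The smallest significant d is √(3 × 3.009/233) = 0.197.
- The shifted estimate is d − 0.35·delta, so significance is lost at delta = (d − 0.197)/0.35.

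| Observed d | Delta at which the overall test is lost |
|---|---|
| 0.20 | 0.01 SD |
| 0.25 | 0.15 SD |
| 0.30 | 0.29 SD |
| 0.35 | 0.44 SD |

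- At d = 0.25, delta of 0, 0.1 and 0.2 gives F = 4.85, 3.59 and 2.52, with p = 0.008, 0.028 and 0.081.
- With 25% loss (268 per arm, threshold 0.183) delta is 0.27 SD. With 45% loss (197 per arm, threshold 0.214) it is 0.08 SD.
- One pairwise test at z = 1.96 is lost at (0.25 − 1.96 × √(2/233))/0.35 = 0.195 SD, so the overall gate fails first.
- An equal shift in all arms, at equal loss, cancels.

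**5. Tipping point if other visits are used.** Assumptions: 358 per arm, monotone loss of 15/35/45% at months 1/6/12 (55% seen at all three visits, 10% at months 1 and 6, 20% at month 1 only), and one common correlation between visits. Sum 358 × (pattern fraction) × (inverse correlation matrix of the observed visits). Inverting the sum gives the variance of the month-6 mean, and its reciprocal is the effective n per arm.

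| Correlation | Effective n | Threshold d | Delta at d = 0.25 |
|---|---|---|---|
| 0.5 | 247 | 0.191 | 0.17 SD |
| 0.6 | 254 | 0.188 | 0.18 SD |
| 0.7 | 263 | 0.185 | 0.19 SD |

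**6. What the group coefficient estimates.**
- *Only month 6 enters.* It is the month-6 effect. With one record per patient, the patient random effect cannot be separated from residual error, and patients without that score contribute nothing.
- *Several visits enter with only the listed fixed factors.* It is a weighted average over visits. At correlation 0.6, each visit of a patient seen k times has weight 1/(1 + 0.6(k − 1)), that is 1, 0.625 and 0.4545 for k = 1, 2 and 3. Month 12: 0.55 × 0.4545 = 0.25. Month 6: 0.25 + 0.10 × 0.625 = 0.3125. Month 1: 0.3125 + 0.20 = 0.5125. Divided by their sum of 1.075, the weights for months 1/6/12 are 0.477/0.291/0.233. Without loss each is 1/3.

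| Assumed effects, months 1/6/12 | No loss | 15/35/45% loss |
|---|---|---|
| 0.10/0.25/0.25 | 0.20 | 0.18 |
| 0/0.25/0.25 | 0.17 | 0.13 |
| 0.40/0.25/0.10 | 0.25 | 0.29 |
| 0.25/0.25/0.25 | 0.25 | 0.25 |

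**The case against.** **The model already handles missing outcomes.** If it is a repeated-measures model with visit terms, it is valid under MAR. The patient random effect and the MAR wording in 5.2.3 suggest that this is meant, and the sentence on contrasts in 5.2.1 may point to visit terms that were not written down. This stands, and it means the documents do not support a reader's inference that the primary analysis is biased or invalid. It does not replace a check of MAR itself.

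**The target is not in doubt.** A reader might infer that the listed model does not estimate the month-6 effect at all. The SAP does not support that. Sections 5.1, 5.2.1 and 5.2.3 all name month 6, section 4.4 keeps months 1 and 12 for secondary endpoints, and with month 6 alone the coefficient is the month-6 effect. The averaging in step 6 arises only if several visits enter without visit terms.

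**The scenario is unfavourable by choice.** Section 4.4 expects the same loss rate in every arm, and nothing in the SAP points to loss that is informative in one arm only. This is fair, and equal shifts do no harm. But equal rates do not imply equal reasons. Sections 4.4 and 5.4 also describe interviews that end and patients who leave the study because of their current state, so some loss may be related to outcome.

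**Ordinary outcome imputation would add little.** Correct: under MAR it repeats the mixed model's assumption. Only the shifted analysis tests it.

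**Conclusion.** The point holds as a cheap improvement. About 375 of 1074 primary outcomes are expected to be missing. The only planned missing-data check does not touch them, so nothing shows whether the conclusion survives a departure from MAR.

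At the design effect, the margin for the overall test is about 0.15 SD in the feedback arm's missing scores with the completers' standard error, or 0.17 to 0.19 SD if other visits are used. These figures illustrate and do not predict: the one-arm shift, correlations and loss pattern are assumptions, and the standard error is held fixed as the shift grows. The margin widens quickly if the observed effect exceeds 0.25.

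Confidence is high for the missing-data part. For the model wording, the finding is ambiguity, not error: the SAP does not settle which visits enter, and the meaning of the group coefficient depends on it. The sample size is unaffected.

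**What to change.** **Section 5.3.** State that the primary analysis assumes MAR. Add a delta-adjusted (tipping-point) multiple imputation of the missing 6-month PHQ-9, by arm, using baseline and any other available PHQ-9 scores. Shift the imputed values by arm over a prespecified grid, for example 0 to 0.5 SD worse in steps of 0.1 SD, and report the overall and pairwise month-6 tests at each step. This also covers patients lost before month 1, who add no follow-up data to any mixed model. The baseline-variable imputation may stay.

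**Section 5.2.1.** State which visits enter. If more than one, include visit and group-by-visit terms, define the overall closed test as the 2-df group contrast at month 6 and the pairwise comparisons as month-6 contrasts, and reconcile this with section 4.4. If only month 6 enters, drop the patient random effect and say that patients without that score do not contribute.

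**Cost.** An amendment to a final, signed SAP (version 2.0) and some extra programming. PHQ-9 at 1, 6 and 12 months is already collected, so no new data are needed. The SAP does not show whether data had been unblinded, so the amendment should record its timing in relation to that. The sensitivity result may be less favourable than the primary one.

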### 5.4 Harms

There is no evidence that feedback concerning depression severity causes suicidality or self-harm; it rather seems that questions of suicidality lower the risk of suicide. To guarantee a safe handling with suicidality any evidence of acute suicidality leads to the immediate information of the GP in every of the three study conditions (including the NO-FEEDBACK condition). If acute suicidality is confirmed by the GP a locally coordinated emergency plan in cooperation with the GPs and centres of psychiatry or rather psychosomatic medicine is introduced. In case of suicidal patients blinding is abolished, treatment is introduced and these patients are excluded from the study. Main risks and obstacles during performing of the study are negative events for the patients. For that reason a suitable monitoring is installed. Monitoring and supervision is being controlled by a specialised company (e.g. Clinical Trials Center (CTC) North). A data handling plan agreeing the DFG guidelines and the Federal Data

Protection Act is going to be published beforehand and ensures data availability, transparency and repeatability. Furthermore, the study follows international guidelines such as ICH-GCP (CHMP, 2016) as well as the guidelines and SOPs of the University Medical Centre Hamburg-Eppendorf.

## 5.5 Statistical software

- STATA 14 or newer
- R 3.4.1 or newer
- SPSS 22.0 or newer

